 Syneron Medical Ltd. Confidential	Clinical Study to Evaluate the Safety and Efficacy of the UltraShape Power Device Using the U-Sculpt Power Transducer for Abdominal Fat and Circumference Reduction			
	Protocol #	DHF21621	Rev. Date	April 05, 2016

	7. Subject improvement and satisfaction: Improvement and satisfaction assessment will be performed independently by the subject himself using a pre-defined scale questionnaire. The subjects will answer this questionnaire at each follow-up visit (4wk FU, 8wk FU and 12wk FU)
Efficacy Endpoints	Primary and secondary objectives will be measured using the next efficacy endpoints: 
 1. Fat thickness measurements using Ultrasound device 2. Fat thickness measurements using calibrated Caliper 3. Circumference measurements of the abdominal area using Measuring Tape 4. Investigator satisfaction using a pre-defined scale 5. Subject improvement and satisfaction using a pre-defined scale 6. Photography
Safety Endpoints	
 1. The number, severity and type of any adverse event recorded throughout the study and post treatment (immediate and delayed response) 2. Pain assessment using NSR scale
Statistical Methods	Descriptive statistics will be used to present changes in the assessments along the study course. Circumference measurements and subject assessments' and satisfaction data will be analyzed using two-tailed Wilcoxon Signed Rank test and/or paired t-test (alpha=0.05) to analyze the data difference from baseline and longitudinal change.

INTRODUCTION AND RATIONALE

Background

Adipose tissue is a loose type of connective tissue specialized to store lipids. The majority of lipids stored in adipose cells are triglycerides formed from imported free fatty acids and glycerol. It is not uniformly distributed in the body. The major adipose depot is subcutaneous (about 80% of all body fat).¹ In men it normally represents 15-20% of body weight and in women, 20-25% of body weight. A certain amount of body fat is necessary for normal female reproduction and health. Subcutaneous adipose tissue helps to shape, cushion and insulate the body and provides padding to some organs.

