Assure repeatable marking of treatment area at each treatment visit

STUDY DESIGN OVERVIEW

This study is a prospective, baseline controlled, multi-center, one arm clinical study showing the performance and safety of the UltraShape Power treatment for abdominal non-invasive fat and circumference reduction.

Up to 120 Healthy subjects in up to 10 investigational sites will be enrolled in this study. All subjects will undergo an assessment of their general health. During the treatment period, subject’s fat thickness and circumference will be measured and three successive bi-weekly (two weeks interval) treatments will be performed.

The study subjects will undergo treatments with UltraShape Power device utilizing the U-Sculpt Power Transducer.

During the follow-up period visit will be conducted as follow: 4 weeks (4wk FU), 8 weeks (8wk FU) and 12 weeks (12wk FU) post last treatment (Tx.3). Subject’s fat thickness will be measured in two different methods (Caliper & Ultrasound) and fat reduction will be assessed at each post baseline visit. Circumference will be measured in 3 measurements heights and circumference reduction will be assessed at each post baseline visit. Additionally, investigator and subject questionnaires will be completed. Finally, photography will be performed under visible light conditions of the front, right, left and back view. Most of the assessments will occur at each of the visits to the clinic.

SUTDY OBJECTIVE

The objective of this trial is to evaluate the safety and efficacy of the UltraShape Power device utilizing the U-Sculpt Power Transducer for abdominal non-invasive fat and circumference reduction

Primary Objective

Statistically significant abdominal fat reduction as measured by Ultrasound device post UltraShape Power treatments at 12 weeks follow-up (12wk FU) versus baseline.

 Syneron Medical Ltd. Confidential	Clinical Study to Evaluate the Safety and Efficacy of the UltraShape Power Device Using the U-Sculpt Power Transducer for Abdominal Fat and Circumference Reduction			
	Protocol #	DHF21621	Rev. Date	April 05, 2016

Primary Safety Objective

1. Evaluate the safety of the treatment with the UltraShape Power device utilizing the U-Sculpt Power Transducer during all study.
2. Comfort level during treatment:
Comfort assessment will be performed independently by the subject himself using NSR scale; the subjects will answer this questionnaire after each treatment (Tx.1, Tx.2 and Tx.3).

Secondary Objectives

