3. Discomfort (pain) level using a 10-point visual analog scale will also be recorded after each benign pigmented lesion clearance treatment– by Numerical Scale Response (NSR), according to Appendix IIIAppendix III - Pain assessment.

STUDY POPULATION

Number of Subjects

This study will be comprised of up to 120 subjects in up to ten (10) investigational sites. Subjects who meet all the inclusion and none of the exclusion criteria will be enroll.

Subject Withdrawal and Replacement

Subjects enrolled in the study can discontinue their participation at any time for any reason without prejudice or reduction in the quality of their medical care. The investigators or sponsor can terminate a subject's participation in this study to protect the subject's health or if the subject fails to follow directions resulting in noncompliance to study procedures. Subjects who withdraw or are terminated from the study may be replaced to ensure at least 120 subjects have completed the study. Subjects who fail to complete the treatment will be replaced and will not be evaluable.

Inclusion Criteria

A subject is eligible to participate in the study if he/she meets all the following inclusion criteria:

1. Signed informed consent to participate in the study.
2. Female and male subjects, ≥ 18 and ≤ 60 years of age at the time of enrolment
3. Fitzpatrick Skin Type I to VI.
4. Abdominal fat thickness of at least 1.5 cm (measured by calibrated caliper).
5. BMI interval: $22 \leq \text{BMI} \leq 30$ (normal to overweight, but not obese).
6. If female, not pregnant, lactating and must be either post-menopausal, surgically sterilized, or using a medically acceptable form of birth control at least 3 months prior to enrollment (i.e., oral contraceptives, contraceptive implant, barrier methods with spermicide or abstinence).

 Syneron Medical Ltd. Confidential	Clinical Study to Evaluate the Safety and Efficacy of the UltraShape Power Device Using the U-Sculpt Power Transducer for Abdominal Fat and Circumference Reduction			
	Protocol #	DHF21621	Rev. Date	April 05, 2016

7. In addition, negative urine pregnancy test as tested before each treatment and at the last visit for women with bearing potential (e.g. not menopause).
8. General good health confirmed by medical history and skin examination of the treated area.
9. Willing to follow the treatment and follow-up schedule and post-treatment care instructions.

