15. Childbirth within the last 12 months or breastfeeding women. Any acute or chronic condition which, in the opinion of the investigator, could interfere with the conduct of the study
16. Unstable weight within the last 6 months (i.e., \pm 3% weight change in the prior six months)
17. Inability to comply with circumference measurement procedure (e.g., inability to hold breath for the required duration).
18. Abdominal fat thickness lower than 2.5 cm after strapping.
19. Participation in another clinical study involving same anatomical areas within the last 6 months (or 30 days in case different anatomical areas were treated in previous trial/s).
20. As per the Investigator's discretion, any physical or mental condition which might make it unsafe for the subject to participate in this study.

STUDY PROCEDURES

Enrollment and Screening

During the first visit, the research staff will screen the subject for eligibility to participate. The inclusion/exclusion criteria will be reviewed, the subject's medical history, an examination of the subject's skin in the treatment areas will be conducted.

The subject will review the informed consent form and the study will be explained to the subject including all risks, potential benefits, procedures, visit requirements, and other alternative treatment options. If the subject qualifies and wishes to participate they will complete the ICF with a signature and date. The original will be retained with subject's records and a copy will be provided to the subject.

The following measurements will be performed and recorded at the specified times throughout the study.

Table 2 – Clinical Evaluation Measurements and Tools

Measurement	When to conduct	Method
Height	Baseline	Scale
Weight	Prior to all treatments (Tx.1, Tx.2 & Tx.3), and at all follow-ups visits (4wk FU, 8wk FU & 12wk FU)	Scale
BMI		Calculation
Fat thickness UltraSound measurement	Baseline, Prior to Tx.3, and at all follow-ups visits (4wk FU, 8wk FU & 12wk FU)	Ultrasound device.
Fat thickness Caliper measurement	Prior to all treatments (Tx.1, Tx.2 & Tx.3), and at all follow-ups visits (4wk FU, 8wk FU & 12wk FU).	Caliper
Circumference measurements		Standardized circumference measuring tape
Photographs		Standardized digital photographs
Urine pregnancy test	Prior to all treatments (Tx.1, Tx.2 & Tx.3), and at the last follow-up visit (12wk FU)	Urine pregnancy test

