Figure 9: Patient positioning during circumference measurements (A) and measuring device position around the abdomen (B)

7. The measurement device should be activated at a constant tension to achieve an exact measurement of the circumference (use measurement device supplied by Syneron only).
8. In order to minimize measurement inaccuracies originating from human error, it is recommended that, whenever possible, the same operator re-measures the patient at approximately at the same hour of day (± 3 hours).
9. Patients should be under fasting for at least 3 hours prior to circumference measurement.

Treatment Procedure

Subjects will receive treatments with UltraShape Power device utilizing the U-Sculpt Power Transducer on the anterior abdomen.

Prior to each treatment measurements of weight, fat thickness (both by Ultrasound and Caliper), and abdominal circumference will be done according to the references from the enrollment visit (Baseline/ prior to Tx.1). Only patients who are eligible for treatment will be allowed to undergo the UltraShape Power procedure.

Enrolled subjects will undergo 3 successive bi-weekly (2 weeks interval) treatments (Tx.1, Tx.2 and Tx.3). Additional three (3) visits in the clinic will be occurred to follow-up the abdominal fat and circumference reduction at visits 4, 5 and 6 (4 weeks, 8 weeks and 12 weeks following last treatment).

 Syneron Medical Ltd. Confidential	Clinical Study to Evaluate the Safety and Efficacy of the UltraShape Power Device Using the U-Sculpt Power Transducer for Abdominal Fat and Circumference Reduction			
	Protocol #	DHF21621	Rev. Date	April 05, 2016

UltraShape Power Treatment Procedure

The subject abdomen will be gathered using reusable straps (supplied by Syneron Medical), to gather the fat area for treatment according to the instruction written in the User Manual.

According to size of the treatment area, the UltraShape Power device will determine the total number of FTZs to be delivered during treatment. While the recommended minimal number of ultrasound FTZs to be delivered per subject at a whole single treatment will be defined / determined by the system according to the subject physical characteristic and treated area size. Prior to admitting the FTZs (pulses) Parker acoustic gel will be applied and on the treated area and used as a coupler agent between the ultrasonic U-Sculpt Power Transducer and the skin surface.

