All data will be recorded on site source documents and transcribed onto Case Report Forms (CRFs). The site will be monitored by Syneron staff or designees to assure adherence to the clinical trial requirements, subject safety, protocol procedures, and for data accuracy. The Case Report Forms and images will be reviewed and retrieved during the monitoring visit. All source documentation will remain in the subject's files at the site.

Review and Analysis of all data collected will be conducted by the Sponsor or designee as described for this protocol with the following data:

Demography and Baseline Measurements

Demographic and baseline/screening measurements (e.g., weight, height and digital images) will be collected and descriptively presented.

Treatment Visit

Skin assessment by the PI, photographs of the treated region, and pain scores will be collected used to document any adverse events to assess the device performance.

Follow-up Visit Measurements

Follow-up measurements for weight, circumference and digital images will be used for comparative measurements with their respective measurement at baseline. Primary endpoints will be evaluated 12 weeks post last treatment (Tx.3). Secondary endpoints may be evaluated at all visits.

 Syneron Medical Ltd. Confidential	Clinical Study to Evaluate the Safety and Efficacy of the UltraShape Power Device Using the U-Sculpt Power Transducer for Abdominal Fat and Circumference Reduction			
	Protocol #	DHF21621	Rev. Date	April 05, 2016

Safety

Safety of device procedure will be evaluated through skin assessments by the PI and research staff. The occurrence and severity of all complications from the start of the study will be recorded.

Protocol Revisions and/or Deviations

With the exception of emergency situations, no changes or deviations in the conduct of this protocol will be permitted without the prior approval of the sponsor.

The IRB/IEC that granted original approval for the study must be notified of all changes in the protocol, and will approve any change or deviation that may increase risk to the subject, and/or that may adversely affect the rights of the subject or validity of the investigation.

In the event of an emergency, the Investigator will institute any medical procedures deemed appropriate. However, all such procedures must be promptly reported to the sponsor and the IRB/IEC.

ADVERSE EVENTS (AE)

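### The paired tests named for circumference drop a subject who misses week 12 from the 12-week comparison; a repeated-measures model would use that subject's earlier readings

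*Combined protocol and SAP*

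**What the plan says.** The only inferential text is the Statistical Methods row of Table 1 (Study Synopsis). It opens "Circumference measurements and subject assessments' and satisfaction data will be analyzed using" and then names a "two-tailed Wilcoxon Signed Rank test and/or paired t-test (alpha=0.05) to analyze the data difference from baseline and longitudinal change". Fat thickness, by ultrasound or caliper, is not in that sentence.

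Table 2 schedules caliper and circumference "Prior to all treatments (Tx.1, Tx.2 & Tx.3), and at all follow-ups visits (4wk FU, 8wk FU & 12wk FU"), which makes six visits. It schedules ultrasound at "Baseline, Prior to Tx.3, and at all follow-ups visits (4wk FU, 8wk FU & 12wk FU"), which makes five. The Treatment Procedure section instead says "Prior to each treatment measurements of weight, fat thickness (both by Ultrasound and Caliper), and abdominal circumference will be done", which would make six for ultrasound too. The argument below does not depend on which is right.

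The primary objective in the body text is "Statistically significant abdominal fat reduction as measured by Ultrasound device post UltraShape Power treatments at 12 weeks follow-up (12wk FU) versus baseline". The Follow-up Visit Measurements paragraph adds: "Primary endpoints will be evaluated 12 weeks post last treatment (Tx.3). Secondary endpoints may be evaluated at all visits". The secondary objectives compare each earlier visit with baseline.

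On incomplete subjects, Subject Withdrawal and Replacement says: "Subjects who withdraw or are terminated from the study may be replaced to ensure at least 120 subjects have completed the study". It declares non-evaluable only those who do not complete treatment. The Case Report Forms section asks that missing data be explained. No repeated-measures model, imputation rule or analysis set is given.

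**The concern.** Both named tests compare two readings per subject, so neither is a method for a course over six visits. Take a subject who had all three treatments, attended at 4 and 8 weeks, and missed week 12. That subject cannot enter a paired 12-week comparison. This is how a paired test behaves when no missing-data rule exists.

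The earlier readings still count in their own secondary comparisons with baseline. They do not inform the 12-week estimate, although they carry information about it.

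What is at stake is mainly bias. If disappointed subjects are less likely to come back, those who attend at week 12 are a favourable selection. With no comparator arm, nothing offsets that, and it is read as reduction due to the device. Replacement can restore the number of completers, but it adds more attenders and so does not remove the selection.

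**Working it through.** The documents give no dropout rate, SD, correlation, effect size or sample-size derivation, so there is no figure to reproduce. Everything below except the 120 subjects and the two-tailed 0.05 level is an assumption.

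**Inputs.** N = 120. True mean change is zero, in units of the SD of change. A fraction d of week-12 readings is missing. The correlation between the 8- and 12-week changes is r. The log-odds of missing week 12 rise by k for each SD of less reduction at week 8. A two-tailed 0.05 test leaves 2.5% for a false reduction.

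**Bias of the paired mean.** With logistic missingness, the mean 8-week change among attenders is shifted by about k × d(1 − d)/(1 − d) = k × d. The 12-week mean is shifted by r times that:

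bias ≈ r × k × d

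**False-reduction rate.** With n = N(1 − d) attenders the standard error is 1/√n, so

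rate ≈ Φ(−1.96 + bias × √n)

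For k = 0.5:

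| r | d | n | bias (SD) | bias × √n | rate |
|---|---|---|---|---|---|
| 0.5 | 5% | 114 | 0.0125 | 0.133 | 3.4% |
| 0.5 | 10% | 108 | 0.025 | 0.260 | 4.5% |
| 0.5 | 20% | 96 | 0.050 | 0.490 | 7.1% |
| 0.8 | 5% | 114 | 0.020 | 0.214 | 4.0% |
| 0.8 | 10% | 108 | 0.040 | 0.416 | 6.1% |
| 0.8 | 15% | 102 | 0.060 | 0.606 | 8.8% |
| 0.8 | 20% | 96 | 0.080 | 0.784 | 12.0% |

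Simulation with 4,000 trials per setting agrees. At r = 0.5 the rates are 3.3%, 4.3% and about 7% for 5, 10 and 20% missing. At r = 0.8 they are 3.9, 5.7, 8.6 and 11.6% for 5, 10, 15 and 20% missing.

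For k = 1.0 the approximation runs high, so simulation is used. At r = 0.8 the rate is about 6, 12, 19 and 28% for 5, 10, 15 and 20% missing.

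A likelihood-based estimate that also uses weeks 4 and 8 was biased by at most about 0.003 SD at r = 0.8. Its false-reduction rate, with its own standard error, was about 2.5%.

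**Random missingness (k = 0).** Neither method is biased. Taking the earlier change as one predictor, the model's effective sample size is 1/[(1 − r²)/n + r²/N].
- r = 0.8, 10% missing: 1/(0.36/108 + 0.64/120) = 115.4 against 108. The standard error ratio is √(108/115.4) = 0.967, about 3% smaller.
- r = 0.8, 20% missing: 1/(0.36/96 + 0.64/120) = 110.1 against 96. The ratio is √(96/110.1) = 0.934, about 7% smaller.

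**No missing readings.** n = N, and both methods give the same 12-week mean change.

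**The case against.** The strongest reply is that paired tests fit the objectives as written. Each fat and circumference objective is one named visit against baseline, and the reference to longitudinal change may mean no more than that series. This stands in part. Nothing in the plan asks for testing every pair of visits, so counting all possible pairs would be unfair. It does not answer how the 12-week estimate treats subjects who lack that reading.

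Three stronger readings are tempting, and the documents do not support them:
- A reader might infer that the plan assigns paired tests to the primary endpoint. The sentence covers circumference and subject questionnaires only. That no test is named for fat thickness is a separate and larger gap.
- A reader might infer that the intermediate visits go unused. They enter their own secondary comparisons.
- A reader might infer that the plan excludes or replaces a subject who misses week 12. No such exclusion is stated, and replacement covers withdrawal or termination, which one missed visit need not be.

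It is also fair to say that the size rests on assumptions. Follow-up is short, with windows of ±7 days, so few readings may be missing. The documents give no evidence that missing visits would depend on outcome.

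**Conclusion.** The point holds for circumference as written, and for ultrasound and caliper fat thickness only if the same tests are carried over. The 12-week comparison would use only subjects with both readings, and the plan offers no method to bring in the others' earlier data.

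With 5–20% missing, correlation 0.5–0.8 and a log-odds slope of 0.5 per SD, the bias is about 0.01–0.08 SD toward the device. The false-reduction rate is between little above 2.5% and about 12%. A slope of 1.0 takes it to about 28% in the worst setting examined. If missingness is random, the only loss is precision, up to about 7% in the standard error. If nothing is missing, nothing is lost.

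This does not show that the trial's result would be biased. It shows that the stated method has no protection against a plausible mechanism, when the data for some protection are already being collected.

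**What to change.** For circumference, state that the 12-week-minus-baseline contrast and its 95% confidence interval come from a mixed model for repeated measures. All visits including baseline form the response, visit is a categorical effect, and the within-subject covariance is unstructured. Use the same model for ultrasound and caliper fat thickness if that approach is adopted for them. Keep the paired test on subjects with a week-12 reading as a sensitivity analysis.

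Do not apply this model to the questionnaires. They are four-level ordinal scales collected at the three follow-up visits, with no baseline.

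The cost is analysis-plan wording and a standard model fit, with no new visits or data. The downside is reliance on missingness being random given the observed readings. That is a weaker assumption than the complete-pair comparison needs, but it would not fully protect against missingness that depends on the unseen week-12 value.

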Study Population	Up to 120 healthy adult volunteers, seeking for noninvasive abdominal fat and circumference reduction, male and females, 18 to 60 years of age from up to 10 investigational sites.
Treatment and Duration	
Eligible subjects will receive 3 bi-weekly treatments (2 weeks interval) with the UltraShape Power device utilizing the U-Sculpt Power Transducer according to the study protocol.
 
The subject will return for 3 follow up visits: four weeks (4wk FU), eight weeks (8wk FU) and 12 weeks (12wk FU) after the last treatment (Third Treatment).
 
Each subject will be enrolled for total expected study duration of 16 weeks.

Objective	The objective of this trial is to evaluate the safety and efficacy of the UltraShape Power device utilizing the U-Sculpt Power Transducer for abdominal non-invasive fat and circumference reduction
Primary Objective	Statistically significant abdominal fat reduction post UltraShape Power treatments at 12 weeks follow-up (12wk FU) versus baseline
Primary Safety Objective	
 Evaluate the safety of the treatment with the UltraShape Power device utilizing the U-Sculpt Power Transducer during all study Comfort level during treatment: Comfort assessment will be performed independently by the subject himself using NSR scale. The subjects will answer this questionnaire after each treatment (Tx.1, Tx.2 and Tx.3)
Secondary Objectives	
 Statistically significant abdominal fat reduction post UltraShape Power treatments as measured by Ultrasound device at Pre Tx.3, 4 weeks, and 8 weeks follow-up (4wk FU and 8wk FU) versus baseline Statistically significant abdominal fat reduction post UltraShape Power treatments as measured by calibrated Caliper at Pre Tx.2, Pre Tx.3, 4 weeks, 8 weeks and 12 weeks follow-up (4wk FU, 8wk FU and 12wk FU) versus baseline Statistically significant abdominal circumference reduction post UltraShape Power treatment/s at Pre Tx.2, Pre Tx.3, 4 weeks, 8 weeks and 12 weeks follow-up (4wk FU, 8wk FU and 12wk FU) versus baseline Investigator satisfaction: Satisfaction assessment will be performed by the study investigator using a pre-defined scale questionnaire. The investigator will answer this questionnaire at each follow-up visit (4wk FU, 8wk FU and 12wk FU)

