The Study Personnel will obtain written Informed Consent prior to the subject’s participation in any study procedures. The Study Personnel will inform the subjects of the experimental procedure to be utilized and assure the subjects that their decision regarding participation in the study will have no bearing on the quality of medical care received and that their decision whether to participate in the study is strictly voluntary.

During the initial interview, the subject will be assured that they are free to change their mind and will be allowed to participate in the study or withdraw from the study with no adverse effect on their standard medical care.

Monitoring Plan

At least 3 monitoring visits are projected during the whole study. The frequency of which will be based on enrolment, study activities and the study visit scheduled. The first visit is scheduled at the initiation of the study prior to the first subject treatment in the study. The second visit is scheduled after enrolment and treatment has been initiated and a third visit will be for a close-out visit for the study. Interim visits may be conducted as needed to assure compliance to the study protocol and regulatory requirements. The number and frequency of monitoring visits may also be increased per the sponsor decision to collect data and images post treatment.

Case Report Forms

Paper case report forms will be used in this trial. All protocol-required information collected during the study must be entered in the appropriate field of the case report form (CRF). The investigator, or designated representative, should complete the appropriate CRF fields as soon as possible after information is collected. The information must match the information that exists as source documents in the clinic chart, hospital chart, and/or investigator’s files. An explanation should be given for all missing data.

It is the investigator’s responsibility to assure the accurate completion, review, and approval of all CRFs and the timely completion and submission of all adverse event forms.

Record Maintenance

The investigator shall retain a copy of all study documents in accordance with the FDA regulations which specify that records should be kept for a period of two years: 1) following the date a marketing application either is approved or disapproved for the use, or 2) following notification to FDA that no application is being filed and/or that the study has been discontinued.

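### Treatment non-completers are declared not evaluable whatever the reason, no all-treated or safety set is defined, and the two statements of 120 subjects agree only if nobody drops out

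*Combined protocol and SAP*

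**What the plan says.** Three statements on numbers set a ceiling. Synopsis, Study Population: "Up to 120 healthy adult volunteers". Study Design Overview: "Up to 120 Healthy subjects in up to 10 investigational sites will be enrolled in this study". Number of Subjects: "This study will be comprised of up to 120 subjects in up to ten (10) investigational sites".

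The section Subject Withdrawal and Replacement sets a floor: subjects who withdraw or are terminated "may be replaced to ensure at least 120 subjects have completed the study". Its next sentence reads: "Subjects who fail to complete the treatment will be replaced and will not be evaluable". Earlier in the same paragraph, subjects may leave for any reason, and "The investigators or sponsor can terminate a subject's participation in this study to protect the subject's health".

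On analysis, the Synopsis (Statistical Methods) names a two-tailed signed-rank test and/or a paired t-test at alpha 0.05 for circumference and the subject assessments. It does not mention ultrasound fat thickness, which is the primary measure. Neither that entry nor the Data Analysis section names an analysis population or a method for missing values. The nearest statement is in Case Report Forms: "An explanation should be given for all missing data".

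On safety, Primary Safety Endpoint and the Safety part of Data Analysis require events to be recorded throughout the study. Neither says which subjects form the denominator.

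**The concern.** The study has no control arm, so its efficacy result is the mean change from baseline in whoever is analysed. The rule fixes that group by something that happens after treatment begins. Subjects who stop because of a poor response, intolerance, or a decision to protect their health are all removed, and others take their place. An effect among subjects who receive all three treatments is a legitimate, narrower target, but the plan does not say that this is its target.

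Subjects who finish Tx.3 but miss week 12 are not covered by the sentence. They would probably be lost too, because the only tests named need both values of a pair, but that is an inference.

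The rule is also not confined to efficacy. With no safety set defined, it is unclear whether a replaced subject counts in the adverse-event summary.

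Finally, sites need to know when to stop enrolling. Once 120 subjects are enrolled and one stops treatment, the enrolment ceiling, the completer floor and the replacement rule cannot all be followed.

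**Working it through.** **Inputs from the documents.** Enrolment ceiling 120 (Synopsis, Study Design Overview, Number of Subjects); completer floor 120 (Subject Withdrawal and Replacement); three treatments (Synopsis); primary assessment 12 weeks after Tx.3 (Follow-up Visit Measurements).

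**Assumed inputs.** The documents give no drop-out rate, effect size or standard deviation. I use d = 2%, 5%, 10% and 20%. In step 1, d is the share not completing the study; in steps 2 and 3 it is the share not completing treatment. The low value is included because the Risks section reports only mild, resolved adverse events across UltraShape devices and says the Power device itself had been used in previous studies.

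**Step 1: the two uses of 120.** The figure cannot be re-derived, because two-sided alpha is given but power, effect size and standard deviation are not. What can be checked is whether ceiling and floor agree. Enrolment needed for 120 completers is 120/(1 − d), rounded up. At d = 0 this is 120, so the statements agree only then.

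| d | Enrolment for 120 completers | Completers if 120 is the ceiling |
|---|---|---|
| 2% | 123 | 117.6 |
| 5% | 127 | 114 |
| 10% | 134 | 108 |
| 20% | 150 | 96 |

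The chance that none of 120 subjects drops out is (1 − d)^120: 8.9% at 2% and 0.2% at 5%.

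**Step 2: effect on the mean.** Let r be the mean change in non-completers divided by that in completers. The all-treated mean is (1 − d + d·r) times the completer mean, so the completer mean differs from the all-treated mean by 1/(1 − d + d·r) − 1. At d = 10%: with r = 0, 1/0.90 − 1 = +11.1%; with r = 1.5, 1/(0.90 + 0.15) − 1 = 1/1.05 − 1 = −4.8%.

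| d | r = 0 | r = 1.5 |
|---|---|---|
| 2% | +2.0% | −1.0% |
| 5% | +5.3% | −2.4% |
| 10% | +11.1% | −4.8% |
| 20% | +25.0% | −9.1% |

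The sign depends on r, about which the documents say nothing.

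**Step 3: the safety denominator, as an illustration.** At d = 10% with 120 treatment completers, 134 − 120 = 14 treated subjects did not complete. If all 14 stopped for an adverse event and no completer had one, the rate is 0/120 = 0% in completers and 14/134 = 10.4% in all treated. If 7 of the 14 did, the second figure is 7/134 = 5.2%. These are constructed cases; they show only that the choice of denominator can matter.

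**The case against.** The strongest reply is that the plan already implies a completer target: it declares non-completers not evaluable in advance and sets the primary endpoint 12 weeks after Tx.3. That is a fair reading, and such a target can be defended. What remains is that the plan never states it, gives no all-treated result beside it, and does not confine the rule to efficacy.

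It can also be said that drop-out may be low. That is so, and at 2% the mean shifts by 2.0% or less in the cases above. But the missing definitions and the conflict over 120 do not depend on the rate.

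Three stronger readings are tempting and are not supported:

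- A reader might infer that adverse events in non-completers are discarded. The documents require events to be recorded throughout and nowhere say they are dropped. The gap is in the summary's denominator.
- A reader might infer that the rule inflates the effect, or that the primary test would fail in all treated subjects. The direction is unknown, and without an effect size or standard deviation nothing can be concluded about significance.
- A reader might see a contradiction in replacement being optional in one sentence and mandatory in the next. These can be read as a general rule and a specific one for treatment non-completers. A subject who withdraws during treatment falls under both, so the wording deserves tidying, but it is a minor matter.

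**Conclusion.** The point stands and should be fixed. As written, the plan removes every treatment non-completer from evaluation, including those stopped to protect their health, and states no all-treated set, safety set or missing-data rule. The primary 12-week ultrasound change is then open to bias of unknown sign and size. Its scale depends on the assumed rate and on how non-completers changed: at 5% to 20% non-completion, from 5.3% to 25.0% too high relative to the all-treated mean if they had zero change, and from 2.4% to 9.1% too low if they changed 1.5 times as much as completers.

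For safety, the finding is limited to an undefined denominator. The conflict between the enrolment ceiling and the completer floor needs no assumption: any drop-out breaks one of them. Only the size of the gap rests on the assumed rates.

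**What to change.** 1. In Subject Withdrawal and Replacement, delete the statement that non-completers are not evaluable, and say that replacement does not remove a treated subject from the analysis. Subjects who leave before Tx.1 (the Screening section allows up to 14 days before the baseline and treatment visit) then fall outside both sets below.
2. Define the safety set as every subject who received any part of one treatment.
3. Define the efficacy set as every treated subject with a baseline ultrasound value, and use all available scheduled ultrasound values. Ask subjects who stop treatment but remain in the study to attend the follow-up visits already scheduled. For missing week-12 values, add a sensitivity analysis assuming zero mean change. Report completers of all three treatments as a supporting analysis. The follow-up and the sensitivity analysis carry most of the weight: under Tables 2 and 3, a subject who stops before the Tx.3 visit otherwise has no post-baseline ultrasound value.
4. State one size. Either 120 is the enrolment limit and the completer floor is deleted, or 120 is the completer target and the enrolment figure is restated in the Synopsis, Study Design Overview and Number of Subjects.

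**Cost.** Mostly wording, plus follow-up effort that the withdrawal paragraph does not now describe, and a possibly less favourable estimate. If 120 stays the limit, the standard error relative to 120 completers with the same standard deviation grows by √(1/(1 − d)): 2.6%, 5.4% or 11.8% at 5%, 10% or 20% attrition. If 120 is the completer target, 7, 14 or 30 more subjects are needed.

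Two neighbouring inconsistencies are separate points to reconcile. Return Visits counts 12 weeks from the last treatment, while the Synopsis, Study Design Overview and Follow-up Visit Measurements tie it to Tx.3. Treatment Procedure calls for ultrasound before each treatment, while Secondary Objectives and Tables 2 and 3 show none before Tx.2.
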